#### 26 Summary of changes to the statistical analysis plan

The original statistical analysis plan is described in the original protocol, version 1.2 provided below.

Before any unblinding of treatment groups was performed, the final statistical analysis plan was uploaded to clinicaltrials.gov. All analyses were carried out with the treatment groups still blinded and labeled as "treatment group A" and "treatment group B". If requested, the Email correspondence with the unblinded nurse regarding unblinding can be forwarded.

33

In the original statistical analysis plan missing data were handled by last observation carried forward. However, a decision was made to use mixed model of repeated measurements to reduce the risk of bias. Mixed model was used for all analyses including the primary endpoint (change in glucose tolerance).

38

Furthermore, the study was intended to be exploratory with an estimated sample size of 100 participants. However, it was possible to perform a precise power calculation based on unpublished baseline data from individuals with and without impaired glucose tolerance (IGT) following a 4hour 75-grams OGTT from the study: "The Impact of Liraglutide on Glucose Tolerance and the Risk of Type 2 Diabetes in Women With Previous Pregnancy-induced Diabetes".(1)

43 Risk of Type 2 Diabetes in women with Previous Pregnancy-induced Diabetes".(1)

44 The power calculation resulted in a sample size of 96 participants, similar to the initial estimation.

45

46 Reference List

Foghsgaard S, Vedtofte L, Mathiesen ER et al. The effect of a glucagon-like peptide-1 receptor
agonist on glucose tolerance in women with previous gestational diabetes mellitus: protocol for an
investigator-initiated, randomised, placebo-controlled, double-blinded, parallel intervention trial.
BMJ Open 2013;3(10):e003834.

- 51
- 52
- 53

54

### 57 Final statistical analysis plan

58

#### 59 Power calculation

A sample size of 96 participants (48 in each group) was estimated, with two-sided t-testing, an  $\alpha$  of 60 61 5% and a power of 90%. The power calculation was based on the primary outcome measurement: 62 Change in glucose tolerance. The glucose tolerance was estimated by the total Area Under the 63 Curve (AUC) following a 4-hour 75-grams Oral Glucose Tolerance Test (OGTT). The expected mean total AUC for the plasma glucose excursion following a 4-hour 75-grams OGTT was 64 65 estimated as 1695 (SD 158) and 1800 (SD 158) after 16 weeks of treatment for the liraglutide and liraglutide placebo group, respectively. The difference in total AUC was based on unpublished data 66 in individuals with and without Impaired Glucose Tolerance (IGT) following a 4-hour 75-grams 67 68 OGTT at baseline from the study: "The Impact of Liraglutide on Glucose Tolerance and the Risk of Type 2 Diabetes in Women With Previous Pregnancy-induced Diabetes".(1) 69

70

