#### 71 Procedure

All analyses will be carried out with the treatment groups still blinded and labeled as "treatment group A" and "treatment group B". Before dividing participants into group A and group B, the statistical plan was completed and uploaded on clinicaltrials.gov, and the data set was locked. The final unblinding of treatment groups (liraglutide or liraglutide placebo), will not be carried out until all statistical analyses are performed. All analyses will be performed using SAS 9.4, with  $\alpha$  set at 0.05 and two-sided testing.

All efficacy analyses will be performed using a modified intention-to-treat principle. All participants who were randomized, received at least one dose of the trial compound (liraglutide or liraglutide placebo) and who had at least one assessment after baseline will be included in the efficacy analyses. All safety analyses will be performed in the intent-to-treat sample that includes all participants, who were randomized and received at least one dose of the trial compound (liraglutide or liraglutide placebo).

84

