### 519 4.1 Number of patients and target population

Planned number of subjects to be screened (i.e. documented informed consent): 150 (Screen failure rate =
15-20 %). Number of subjects planned to be randomized and started on trial product: 125. Number of
subjects expected to complete the trial: 100.

523 Hundred patients will be included. The patients will be recruited via Psychiatric Center Copenhagen or via 524 other psychiatric centres in the Capitol Region of Copenhagen. Recruitment will take place through direct 525 contact or through contact by mail or telephone. The expected number of dropouts is difficult to estimate, 526 since similar interventions with daily subcutaneous injections have not, to our knowledge, been performed 527 before among psychiatric patients. In the study by Astrup et al., 16 persons out of 90 (18%) in the 528 liraglutide, 1.8 mg group over the 20 weeks trial period. We will expect the withdraw to be a little higher in 529 our patient population over time, but this effect is expected to be counteracted by our shorter study 530 duration. Consequently, we expect a drop-out rate of 20 % in our study population over the 16 weeks trial 531 period. At least eighty patients have to complete the full 16 week trial. If the drop out rate should turn out to be higher than 20 %, more patients will be included in order to reach the goal of eighty patients 532 533 completing the study. In that case change in sample size will be documented in a substantial protocol 534 amendment.

535

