### 577 **4.5 Patient withdrawal**

578 Completion or trial termination for any reason will be fully documented in the clinical record form (CRF) 579 pages. Patients are free to withdraw from the trial at any time without providing reason(s) for withdrawal 580 and without prejudice to further treatment. The reason for withdrawal may be withdrawal of consent, 581 treatment failure, adverse event(s), pregnancy discovered during the trial, significant worsening (Clinical 582 Global Impressions-Improvement (CGI-I) score of 6 or 7 (much or very much worse), Change in the dosing of olanzapine or clozapine of more than 20% or loss to follow-up. The reason(s) will be recorded 583 584 in the CRF. Dropouts will be replaced until 80 patients have completed the treatment period. Data from 585 dropouts will be included in data processing. Patients withdrawing from the trial should be encouraged to 586 go through the same final evaluations as patients completing the trial according to the protocol with special 587 focus on safety. The aim is to record data in the same way as for patients who complete the trial. Otherwise 588 data will be recorded as consented by the patient. This will be documented in the CRF.

589

## 590

5

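### The 96 participants for 90% power include no drop-out allowance; the protocol's 80-completer rule supports about 83.5%, and its competing targets need reconciling

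*Supplement*

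**What the plan says.** **Final SAP, Power calculation.** "A sample size of 96 participants (48 in each group) was estimated, with two-sided t-testing", with an alpha of "5% and a power of 90"%. The expected total AUC is "estimated as 1695 (SD 158) and 1800 (SD 158) after 16 weeks of treatment for the liraglutide" and placebo groups respectively. The section gives no drop-out rate and does not say whether the 96 are randomised or evaluable. The summary of SAP changes describes 96 as close to an initial estimate of 100 participants.

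**Final SAP, Procedure.** Tests have alpha "set at 0.05 and two-sided testing". The efficacy set takes in every dosed participant with any assessment after baseline.

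**Protocol version 1.2, section 4.1.** One part reads "Number of subjects planned to be randomized and started on trial product: 125", with 100 expected to complete. The next paragraph says that 100 will be included, that "we expect a drop-out rate of 20 % in our study population", and that "At least eighty patients have to complete the full 16 week trial".

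**Protocol, section 4.5.** "Dropouts will be replaced until 80 patients have completed the treatment period". Patients who withdraw are to be encouraged to attend the final evaluations.

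**Protocol, section 5.2 and Table 1.** The OGTT is done at week 0 and week 16 only.

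**The concern.** The primary endpoint needs a week-16 OGTT, and no OGTT is scheduled between baseline and week 16. A participant who leaves without the final test therefore contributes no post-baseline value to the primary comparison, and a mixed model has no interim OGTT to borrow from. The efficacy set does not show this loss, because a week-4 weight is enough to qualify.

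A sample size with no attrition allowance thus has to be read as a count of final OGTTs. The SAP calls it a count of participants, beside a protocol that expects one in five to drop out and stops replacement at 80 completers. If the trial is described as 90% powered for a 105-unit difference when its completion rule secures only 80 completers, a null result will be read against a type II error of about 10% when the planned figure was nearer 16% to 18%.

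**Working it through.** **Inputs.** Difference 1800 − 1695 = 105; SD 158 in each group; two-sided alpha 0.05; power 90%; 48 per group (all SAP). Drop-out 20%; 125 randomised with 100 completing; 100 included with at least 80 completing (protocol section 4.1). Standardised difference 105/158 = 0.665.

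**Step 1: reproduce the 96.** With the normal approximation,

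n per group = 2 × [158 × (1.960 + 1.282) / 105]² = 47.6, rounded up to 48, or 96 in total.

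The plan's figure is reproduced exactly with no loss. Normal-approximation power at 48 per group is 90.2%. With the noncentral t it is 89.7%, and 49 per group gives 90.3%. That gap is a matter of method and is not a fault.

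**Step 2: power at the numbers the documents give.** The noncentrality parameter is 105 / [158 × √(2/n)] with 2n − 2 degrees of freedom, two-sided 5%.

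| Scenario | Evaluable | Power (t) | Power (normal) |
|---|---|---|---|
| 96 evaluable | 96 | 89.7% | 90.2% |
| 125 randomised, 20% lost (125 × 0.8) | 100 | 90.8% | 91.4% |
| 100 included, 20% lost (100 × 0.8) | 80 | 83.5% | 84.4% |
| 96 randomised, 20% lost (96 × 0.8) | 76.8 | 82.0% | 82.9% |
| 96 randomised, 10% lost (96 × 0.9) | 86.4 | 86.3% | not computed |

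Type II error (t) is 100 − 83.5 = 16.5% at 80 completers, and 100 − 82.0 = 18.0% at 76.8 evaluable.

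**Step 3: number to randomise for 96 evaluable at 20% loss.** 96/0.8 = 120. Starting from the t-based 98, 98/0.8 = 122.5, or 123. Both lie just under the protocol's 125 and well above 100.

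**Step 4: what covariate adjustment could recover.** Assume that SD 158 is the unadjusted week-16 SD. ANCOVA on the baseline value multiplies the variance by 1 − r², where r is the baseline to week-16 correlation. To match 96 unadjusted participants:

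- with 80 evaluable, r = √(1 − 80/96) = 0.41
- with 76.8 evaluable, r = √(1 − 76.8/96) = 0.45

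By the normal approximation, 80 completers give 84.4% at r = 0, 90.0% at r = 0.4 and 92.9% at r = 0.5. The documents give no value of r.

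**The case against.** A reader might infer that the calculation is wrong, or that 90% power cannot be reached under this plan. Neither follows.

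- **The arithmetic is correct.** The 96 reproduces from its inputs.
- **One of the protocol's two plans meets the target.** 125 randomised with 100 completing is exactly a 20% allowance and gives about 91%. The shortfall depends on the 100/80 plan, or on randomising only 96. The documents do not state the latter.
- **The SAP does not equate 96 with 100 enrolled.** It refers to 100 participants, and section 4.1 uses 100 both for those included and for those expected to complete.
- **Eighty is a floor from a protocol planned for 80% power** (section 8.2). On the SAP's inputs, 80 completers exceed that older target.
- **Drop-out need not mean a lost OGTT**, since withdrawals are encouraged to attend the final evaluations.
- **The planned analysis is an ANCOVA**, which may be more precise than the t-test used for sizing.
- **The practical effect is limited.** The SAP was completed around data lock, so its wording could not change recruitment, and planned power alters no estimate or confidence interval.

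These points rule out an unqualified claim of lost power and lower the seriousness. They do not remove the gap. The only replacement rule stops at 80 and was not revisited when the stated power rose to 90%. Attendance after withdrawal is encouraged but not assured, and 10% loss from 96 still leaves 86.3%. No correlation is stated, and the SAP introduces the baseline covariate in a sentence conditional on baseline differences, so its use is not clearly unconditional.

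**Conclusion.** The concern holds in a qualified form. The 96 carries no attrition allowance and supports 90% only if about 96 participants have a week-16 OGTT. At the 80 completers where replacement stops, power is about 83.5%. If 96 are randomised, it is about 82% at 20% loss and 86% at 10% loss. Under the 125/100 plan the 90% is met.

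These figures use the SAP's difference and SD, equal groups, an unadjusted t-test and the protocol's 20%, which is the only drop-out rate stated for this trial. Only protocol version 1.2 is shown. The list of later amendments names no sample-size change, but those versions cannot be checked.

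This is a reporting and consistency fault that should be corrected. It does not invalidate the analysis.

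**What to change.** 1. In the SAP's Power calculation, state that 96 means participants with an evaluable week-16 OGTT.
2. Replace 125/100, 100/80 and 96 with one randomised target and one evaluable target, and align the replacement rule in section 4.5 with them. For reference, 96 evaluable at 20% loss corresponds to 120 randomised.
3. Restate the power for the evaluable number: about 83% to 84% at 80 completers, about 91% at 100.
4. Alternatively, keep 90% by basing it explicitly on the baseline-adjusted ANCOVA. Make the baseline covariate unconditional, and state and justify a baseline to week-16 correlation. About 0.4 is needed at 80 evaluable and 0.45 at 77.

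The cost is wording only, with no extra patients. The drawback is a less favourable stated power, unless the larger evaluable target or the correlation can be supported.

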#### 71 Procedure

All analyses will be carried out with the treatment groups still blinded and labeled as "treatment group A" and "treatment group B". Before dividing participants into group A and group B, the statistical plan was completed and uploaded on clinicaltrials.gov, and the data set was locked. The final unblinding of treatment groups (liraglutide or liraglutide placebo), will not be carried out until all statistical analyses are performed. All analyses will be performed using SAS 9.4, with  $\alpha$  set at 0.05 and two-sided testing.

All efficacy analyses will be performed using a modified intention-to-treat principle. All participants who were randomized, received at least one dose of the trial compound (liraglutide or liraglutide placebo) and who had at least one assessment after baseline will be included in the efficacy analyses. All safety analyses will be performed in the intent-to-treat sample that includes all participants, who were randomized and received at least one dose of the trial compound (liraglutide or liraglutide placebo).

84

#### 85 Primary endpoint

The primary endpoint is the change in glucose tolerance following a 4-hour 75-grams OGTT from

87 week 0 to week 16. During the 4-hour 75-grams OGTT, blood was sampled at fixed time points: -

15, -10, 0, 5, 10, 15, 20, 30, 40, 50, 60, 90, 120, 150, 180, and 240 minutes. An analysis of covariance (ANCOVA) will be use to analyze change in glucose tolerance from week 0 to week 16 using mixed model analyses for the plasma glucose levels for the liraglutide and the liraglutide placebo group, respectively. In case of relevant baseline differences between the two groups, demographic, illness or treatment parameters will be included in the model as fixed effects together with the baseline value of the OGTTs as a covariate.

94

95 Secondary endpoints

96 Blood was also sampled for analyses of C-peptide, glucagon and incretin hormones in response to 97 the glucose load at the same fixed time points during the OGTT. Change in secretion of C-peptide, 98 glucagon and incretin hormones from week 0 to week 16 will also be evaluated using mixed model 99 ANCOVA analyses for the liraglutide and liraglutide placebo group, respectively. In case of 100 relevant baseline differences between the two groups, demographic, illness or treatment parameters 101 will be included in the model as fixed effects together with the baseline value of the relevant 102 variable as a covariate.

103

Most secondary endpoints were repeated every 4 weeks. Few secondary endpoints were only 104 105 repeated at week 0 and 16. For all repeated measurements a mixed model ANCOVA analyses will 106 be use to analyze mean change in continuous outcomes from week 0 to week 16 for the liraglutide and the liraglutide placebo group, respectively. In case of relevant baseline differences between the 107 108 two groups, demographic, illness or treatment parameters will be included in the model as fixed 109 effects together with the baseline value of the relevant variable as a covariate. Change in categorical 110 outcomes from week 0 to week 16 will be analyzed using mixed model logistic regression with the same fixed effects and covariates as described for the continuous outcomes. 111

For secondary endpoints without repeated measurements, missing data imputations will be madeusing Multiple Imputation of Chained Equations (MICE).

114

For continuous outcomes without repeated measurements, outcomes will be analyzed using ANCOVA to detect differences between the liraglutide and the liraglutide placebo group. In the model baseline demographic, illness or treatment parameters will be included. Categorical outcomes without repeated measurements will be analyzed using a multiple mixed effect logistic

regression analysis model, where baseline demographic, illness or treatment parameters will be included.

- 121
- 122
- 123 Subgroup and sensitivity analyses

Subgroup and sensitivity analyses will be performed to assess the robustness of the primary analyses. These analyses will be performed using regression analysis for continuous outcomes and

126 logistic regression for categorical outcomes. The analyses will consider clinically or mechanistically

127 relevant baseline and intra-treatment variables, including:

- 128• Gender
- 129• Smoking

130• Antipsychotics (clozapine vs olanzapine; monopharmacy vs polypharmacy with other antipsychotic

- 131 medications)
- 132• Lipid profile
- 133• Liver function
- 134• Different groups of dysglycaemia:
- 135 a. HbA1c: 43 mmol/mol  $\leq$  HbA1c  $\leq$  47 mmol/mol, vs
- b. Impaired fasting glucose (IFG): Fasting plasma glucose (FPG): 6.1 mmol/l ≤ FPG ≤ 6.9
  mmol/l and HbA1c < 48 mmol/mol, vs

- c. Impaired glucose tolerance (IGT): two-hour plasma glucose after 75-g oral glucose
   tolerance test >7.8 mmol/l with a FPG < 7.0 mmol/l and HbA1c < 48 mmol/mol

- 140• IGT < 11.1 mmol/l vs IGT >11.0 mmol/l
- 141• Liraglutide treatment (1.2 mg vs 1.8 mg liraglutide)
- 142• Weight
- 143• Add-on psychotropic drugs/classes (antidepressants, anxiolytics etc. vs no add-on)
- 144• Antihypertensive treatment vs no antihypertensive treatment
- 145• Lipid lowering treatment vs no lipid lowering treatment
- 146• Changes in antipsychotic medication (> 20 % change in dose vs < 20 % change in dose vs no
- 147 changes in dose for clozapine or olanzapine, respectively)
- 148• Inhalation steroid vs no inhalation steroid
- 149• Body composition
- 150• Insulin resistance

- 151• Beta-cell function
- 152• Incretin hormones
- 153• Psychopathologic rating scales
- 154• Alcohol consumption
- 155• Length of disease
- 156• Diagnosis (schizophrenia vs schizotypal disorder vs paranoid psychosis)
- 157• Side effects
- 158• Serious adverse events
- 159
- 160

161 Summary of changes in the protocol

Protocol	Amendment	Approval from the Danish	Approval from the
version		Health Authority	Ethics Committee
Version 1.2	First final protocol	March 15, 2013	March 27, 2013
Version 1.3	Screening for eligible	N/A. Only the Ethics	August 20, 2013
	patients in hospital	Committee had to approve the	
	records	amendment	
Version 1.4	Sub-study:	December 12, 2013	November 25, 2013
	"Cambridge". Extra		
	blood sampling for		
	proteomic fingerprinting		
Version 1.5	Expansion of	N/A. Only the Ethics	January 16, 2014
	recruitment area. Still	Committee had to approve the	
	single site study	amendment	
Version 2.0	1-year follow-up	September 17, 2014	September 3, 2014
Version 2.1	Adding second site:	January 19, 2015	January 12, 2015
	Aalborg		
Version 3.0	Modification of	June 2, 2015	May 12, 2015
	inclusion criteria:		
	Expansion of definition		
	of prediabetes.		
	Prolongation of study		
	period.		
Version 3.1	Sub-study: Examination	October 23, 2015	October 23, 2015
	of 10 healthy controls		
	for baseline comparisons		
Version 3.2	Prolongation of study	February 22, 2016	February 5, 2016
	period		

166	Original protoc	col, version 1.2			
167					
168	CLINICAL TRIAL	PROTOCOL			
169	. .				
170	Compound	VICTOZA®			
171	B				
1/2	Protocol title				
1/3					
174	Does a GLP-1 recep	otor agonist change	glucose	tolerance in antipsychotic-treated patients?	
1/5	Fully OT when the	2012 000121 21			
1/6	EudraCT number: A	2013-000121-31			
1//		11 1120 2404			
1/8	UIN-number: 011	11-1128-3404			
1/9					
101	Drotocol data/statu	11 1 2012	final (vo	arcian 2)	
101		15 11-1-2013;	iinai (ve	(151011 2)	
102		CATOR			
103	[name]				
104	Professor				
105	Department of Psy	chiatry O	Sign		
100	Department of Fsy Psychiatric Centre	Conenhagen	Jigii.		
188	University of Cone	nhagen Denmark	Date:		
189	onversity of coper	inagen, Dennark	Dute.		
190	CO-INVESTIGATOR	5			
191	[name] MD DI	MSc			
192	Head of Diabetes R	Research Division			
193	Department of Inte	ernal Medicine	Sign:		
194	Gentofte Hospital		0.0.11		
195	University of Coper	nhagen. Denmark	Date:		
196					
197	MONITORATION C	F THE STUDY ACCC	ORDING	TO GCP	
198	The GCP Unit, Univ	versity of Copenhag	en, Bispe	ebjerg Hospital, [name],
199	[name].			
200					
201	FINANCIAL SUPPO	RT			
202	The study has not y	yet received financi	al suppo	ort.	
203					
204	COLLABORATORS				
205	[name], M	D, PhD and [name], MD, PhD, Department of Psychiatry O,	

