### 448 **3.1.1 Primary endpoint**

The primary endpoint is the change in glucose tolerance from baseline (measured by area under the curve (AUC) for the plasma glucose (PG) excursion following a 4-hour 75 g oral glucose tolerance test (OGTT)) to follow up at week 16 or to last observation if study participation is stopped earlier.

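### The SAP's primary-analysis sentence names plasma glucose levels as the modelled response and states no AUC summary or treatment contrast, so it does not fix the AUC difference the trial was powered on as the primary estimate

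*Supplement*

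**What the plan says.** Protocol section 3.1.1 defines the primary endpoint as the change in glucose tolerance from baseline to week 16, "measured by area under the curve (AUC) for the plasma glucose (PG) excursion" in a 4-hour 75 g OGTT. Section 6.1 sets liraglutide against placebo on that measure.

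The final SAP, under Power calculation, uses the same measure: "The glucose tolerance was estimated by the total Area Under the" Curve. It compares expected week-16 means of 1695 and 1800 (SD 158 in each group): "A sample size of 96 participants (48 in each group) was estimated, with two-sided t-testing".

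The SAP's Primary endpoint section lists the sampling times as "15, -10, 0, 5, 10, 15, 20, 30, 40, 50, 60, 90, 120, 150, 180, and 240 minutes" (the first is minus 15). It then says that an ANCOVA will analyse change in glucose tolerance "using mixed model analyses for the plasma glucose levels for the liraglutide and the liraglutide placebo group, respectively". Relevant baseline differences between the groups enter the model as fixed effects, with the baseline OGTT value as covariate. The section does not mention AUC, a treatment term, a treatment-by-time term or a contrast, and does not say which estimate and p-value are primary.

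Among the SAP's descriptions of analyses, an explicit comparative aim, "ANCOVA to detect differences between the liraglutide and the liraglutide placebo group", appears only for continuous outcomes without repeated measurements.

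**The concern.** The endpoint and the power calculation concern one number per OGTT, the AUC. The analysis sentence names the individual glucose levels as the response.

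The levels are also the natural repeated measure. Protocol section 5.2 and Table 1 schedule OGTTs only at weeks 0 and 16. With the baseline value as a covariate, each participant has a single post-baseline AUC, so a repeated-measures model of AUC has nothing to repeat unless week 0 is kept as a response. The SAP does not say that it is.

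An analyst could therefore report an average group effect over sampling times, a group-by-time test or an AUC contrast, and each would fit the sentence. They can give different estimates and p-values for the one primary test. The samples are dense early and sparse late, so an average over samples gives the first hour far more weight than the AUC does.

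**Working it through.** **1. The plan's own figure.** Inputs from the SAP's Power calculation: difference 1800 − 1695 = 105, SD 158, two-sided alpha 5%, power 90%.

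n per arm = 2 × (1.960 + 1.282)² × 158² / 105² ≈ 47.6, so 48 per arm and 96 in total. Power at 48 per arm is 90.2%. With the noncentral t, n is 48.6 and power at 48 per arm is 89.7%. The stated size is reproduced, so the trial is powered on a between-group difference in total AUC. The SAP gives no unit; 1695/240 = 7.1 and 1800/240 = 7.5 are plausible mean glucose values in mmol/L, so I take mmol/L × min.

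**2. Weight of each sampling time in the AUC.** Under the trapezoidal rule, a time's weight is half the sum of its adjacent intervals. Samples at −15 and −10 min have no weight in AUC 0-240.

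| Time (min) | Weight (min) |
|---|---|
| 0 | 2.5 |
| 5, 10, 15 | 5 each |
| 20 | 7.5 |
| 30, 40, 50 | 10 each |
| 60 | 20 |
| 90, 120, 150 | 30 each |
| 180 | 45 |
| 240 | 30 |

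- Up to 60 min: 2.5 + 15 + 7.5 + 30 + 20 = 75, and 75/240 = 31%.
- From 90 min: 90 + 45 + 30 = 165, and 165/240 = 69%.
- Shares of the 16 samples: 11/16 = 69% up to 60 min and 5/16 = 31% from 90 min.
- Without the −15 and −10 min samples: 9/14 = 64% up to 60 min.

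**3. What this does to an estimate.** These effect profiles are assumed, not taken from the documents. The comparison is with an equal-weight average over the 16 samples, multiplied by 240.

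| Assumed 1 mmol/L effect | AUC difference | Implied by sample average | Ratio |
|---|---|---|---|
| 5-60 min only | 75 − 2.5 = 72.5 | 8/16 × 240 = 120 | 1.7 |
| 90-240 min only | 165 | 5/16 × 240 = 75 | 0.45 |
| Constant at all times | 240 | 240 | 1.0 |

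Scaled to the planned difference of 105, a purely early effect would read as 105 × 120/72.5 ≈ 174 and a purely late one as 105 × 75/165 ≈ 48.

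Smoother profiles differ too. For an effect of −1 at 90-180 min, ramping from zero at 60 min and back to zero at 240 min, AUC/240 is −0.56 and the 16-sample mean is −0.25. For an effect in the first 90 min that peaks at 30-60 min, the figures are −0.24 and −0.33.

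**4. Sample size if AUC is named.** Baseline-adjusted ANCOVA multiplies the SD by √(1 − r²), where r is the week-0 to week-16 correlation. The documents do not give r. For r = 0, 0.3, 0.5 and 0.7 the need is 48, 44, 36 and 25 per arm, never above the planned 48.

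**The case against.** The strongest reply is that the sentence says it analyses change in glucose tolerance, which the same SAP ties to total AUC. On that view the glucose levels only name the analyte, since the next paragraph turns to C-peptide, glucagon and incretins. A baseline OGTT value as covariate also fits a summary such as AUC. Moreover, a mixed model over sampling times can return the AUC difference through a weighted contrast. This defeats the stronger claim that the planned analysis cannot estimate the primary endpoint. It does not settle which estimate will be reported, because no summary or contrast is written down.

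A reader might also infer that each group is analysed separately and two within-group changes are reported, open to regression to the mean. The documents do not support that. The power calculation uses the same closing word, respectively, inside a plainly between-group calculation. The primary-endpoint section adjusts a single model for differences between the two groups, and protocol section 6.1 compares liraglutide with placebo. In a randomised between-group comparison the regression-to-the-mean argument falls away.

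It is also fair to say that the SAP nowhere specifies an unweighted mean over 16 samples and that the early-only and late-only profiles are extremes. Both stand. The figures show how far the answers can part, not a predicted bias.

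**Conclusion.** The point holds as under-specification of the primary estimate, with a named response that can lead away from the powered endpoint. It is more than a missing detail: a default group effect averaged over sampling times equals the AUC difference only for special profiles, such as a constant effect. In the illustrations the implied difference runs from 0.45 to 1.7 times the true one.

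Those figures assume equal weighting of samples, as in a marginal group mean from a model with group-by-time terms. Without such terms the weights would follow the covariance structure, and nothing would make them trapezoidal. The effect on power cannot be calculated, because the variances and correlations of the samples are not given.

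The sample size of 96 needs no correction on this account.

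**What to change.** In the SAP's Primary endpoint section, state that the primary estimate is the liraglutide minus placebo difference in change from week 0 to week 16 in total plasma glucose AUC 0-240 min, with 95% CI and two-sided p. Then name one route:

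- a baseline-adjusted model of trapezoidal AUC. A mixed model with week-0 and week-16 AUC both as responses would keep the likelihood-based handling of missing data for which the SAP gave up LOCF; or
- the planned mixed model of glucose levels, with treatment-by-sampling-time effects and the AUC difference taken as their trapezoid-weighted contrast, using the weights above divided by nothing (they sum to 240).

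State how the −15, −10 and 0 min samples form the time-zero value. Replace the closing word of the sentence with the between-group contrast, and do the same where it recurs for the secondary endpoints. If the first route is chosen, keep the time-course model as supportive.

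The cost is SAP wording and a few lines of SAS. No new data or participants are needed.
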